3.2.3 Pharmacokinetic Variables

Pharmacokinetic analysis for AZD9567 will be performed by Covance Clinical Pharmacokinetic Alliance. Pharmacokinetic parameters will be derived using standard non-compartmental methods using WinNonLin version 8.1 or higher (Certara).

The following PK parameters will be calculated:

- AUC_{last} Area under the plasma concentration versus time curve from zero to the last quantifiable concentration
- AUC(0-24) Area under the plasma concentration versus time curve from zero to 24 hours post-dose
- AUC(0-6) Area under the plasma concentration versus time curve from zero to 6 hours post-dose
- C_{max} Maximum observed drug concentration

- t_{max} Time to reach maximum observed drug concentration
- $t_{1/2\lambda z}$ Terminal elimination half-life
- CL/F Apparent total body clearance of drug from plasma after extravascular administration
- V_z/F Apparent volume of distribution following extravascular administration.

Additional PK parameters may be determined.

The following diagnostic parameters will be listed but not summarised:

- λz lower Lower (earlier) t used for λz determination
- λz upper Upper (later) t used for λz determination
- λzN Number of data points used for λz determination
- λz span ratio Time period over which λz was determined as ratio of $t_{1/2}$
- Rsq_adj Statistical measure of fit for the regression used for λz determination adjusted for the number of used data points (n obs).

4 STATISTICAL METHODS

4.1 Data Quality Assurance

TLFs in the report will be checked for consistency, integrity and in accordance with standard Parexel procedures.

4.2 General Presentation Considerations

Summary tables will include the results of each planned sequence in the case of the all randomised subjects set (RND), planned treatment in the case of the Full Analysis Set (FAS) or actual treatment in the case of the Safety Analysis Set (SAF), Per Protocol Analysis Set (PP) and the PK Analysis Set (PKAS).

Non-PK continuous data will be summarised in terms of number of observations, the mean, standard deviation (SD), median, 25th and 75th percentiles (where appropriate), minimum, maximum. In the

case of PK data, the Pharmacokinetics section of this SAP lists the statistics included in the summary tables.

For continuous data, the mean, median and geometric mean will be rounded to one additional decimal place compared to the original data. The SD and geometric coefficient of variation (CV) will be rounded to two additional decimal places compared to the original data. Minimum and maximum will be displayed with the same accuracy as the original data. The maximum number of decimal places reported will be four for any summary statistic.

One decimal will be presented for the geometric CV % included in the PK summary tables.

Categorical data will be summarised in terms of the number of participants, frequency counts and percentages.

Percentages will be presented to one decimal place. Percentages will not be presented for zero counts. Percentages will be calculated using n as the denominator (participants included in the analysis sets or number of non-missing values).

Confidence intervals (CIs) will be presented to one additional place than the original data. P-values greater than or equal to 0.001, in general, will be presented to three decimal places. P-values less than 0.001 will be presented as “<0.001”.

Unless otherwise noted, for the calculation of a change from baseline, the last reliable assessment (in the case of blood pressure, the average of triplicate assessments) prior to the first dose of each study treatment will be considered the baseline measurement.

In the case of assessments at scheduled timepoints, the post-baseline scheduled or non-scheduled reliable assessment closest to the timepoint will be used. If two post-dose assessments are equidistant from a timepoint, the earlier of the two will be used.

All glucose values will be presented in mmol/L. The following formula will be used for the conversion of glucose concentrations from mg/dL to mmol/L:

$$\text{Glucose (mmol/L)} = \text{Glucose (mg/dL)} \times 0.0555$$

All analyses of pharmacodynamics endpoints involving a linear mixed model will be run separately for each cohort.

Change from baseline and percent change from baseline

The change from baseline at each visit will be calculated as:

$$\text{Change from baseline at visit X} = \text{absolute value at visit X} - \text{baseline value}$$

The percent change from baseline will be calculated as:

$$\text{Percent change from baseline} = (\text{change from baseline} / \text{baseline value}) \times 100\%$$

If either a visit value or the baseline visit value is missing, the change from baseline value and the percent change from baseline will be set to missing.

4.3 General Variables

4.3.1 Study Day Definitions

Study day 1 is defined as the date of first dose of study treatment within each treatment period. Within each treatment period, for visits (or events) prior to first dose, study day is defined as ‘date of visit [event] – date of first dose of study treatment’. For visits (or events) that occur on or after first dose of study treatment, study day is defined as ‘date of visit [event] – date of first dose of study treatment + 1’.

“Days since last dose” is defined as ‘date of visit [event]– date of last dose of study treatment’ where “date of last dose” is defined as the date of dosing immediately preceding the event occurrence.

4.3.2 Handling of Missing Data

Unless otherwise stated, missing data will not be imputed.

4.3.2.1 Imputations of Partial Medication and AEs Dates

There will be no imputation of any incomplete dates.

The following rules will be used to determine whether or not an AE has taken place on-treatment:

1. An AE starting from last dose plus 21 days will be considered on-treatment.
2. An AE with an incomplete start date and whose end date is not prior to the time of dosing on Day 1 will be considered to have taken place on-treatment unless the non-missing components of the incomplete start date indicate that the start date falls outside the time from dosing on Day 1 to last dose plus 21 days.

The following rules will be used to assign concomitance to a medication:

1. Exclusively prior medications are those that started and stopped prior to the first dose of the investigational medicinal product (IMP) in the first treatment period and those that started and stopped after 21 days after the last dose in the first period and before the first dose of IMP in the second period. Medications taken between the first dose and up to 21 days after the last dose in any period are concomitant (including medications that started prior to dosing and continued after)
2. A medication with incomplete start and/or end dates will be considered concomitant unless the non-missing components of the incomplete dates indicate that the intake of the medication did not take place between Day 1 and the last dose plus 21 days.

AEs and medications with completely missing end dates will be assumed to be ongoing.

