##### **9.4.3.1 Adverse Events**

The MedDRA will be used to code AEs.

The number of participants experiencing each AE will be summarised by the MedDRA system organ class and preferred term. The number and percentage of participants with AEs in each different category (eg, causally related, severe, etc) will be summarised, and events in each category will be further summarised by MedDRA system organ class and preferred term.

SAEs will be summarised separately if a sufficient number occur.

Any AE occurring before first study intervention will be included in the data listings but will not be included in the summary tables of AEs. AE summary tables will include only AEs occurring after start of study intervention (first dose).

Any AE occurring after last dosing and up to 21 days after discontinuation of study intervention, within each period, will be included in AE summaries. AEs occurring after 21 days will be listed separately, but not included in summaries.

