4.11.1 Adverse Events

Within each cohort, AEs will be assigned as having taken place after each of the two treatments if the start of the AE is after the first dose of the treatment but before the end of 21 days after the last dose (i.e., the end of Day 24, in the case of subjects whose last dose was on Day 3). AEs on Day 1 with a missing start time will be assumed to have started after the first dose.

In order to assign the corresponding SOC and preferred term to each AE, AEs will be coded using the Medical Dictionary for Regulatory Activities (MedDRA) Version 22.1 or higher.

AEs occurring prior to the time of dosing on Day 1 and after 21 days after the last dose will not be included in summaries.

An AE listing for the Safety analysis set will cover details for each individual AE. A summary table with the number of AEs, by SOC and PT will be created.

The following summaries for the number and percentage of participants will be created:

- Number of subjects with adverse events in any of these categories:
 - Any AE
 - Any AE with outcome = death
 - Any SAE (including events with outcome = death)
 - Any AE leading to discontinuation of IP
 - Any AE leading to drug interruption
 - Any AE leading to withdrawal from study
- Number of subjects with adverse events, by SOC and PT
- Number of subjects with adverse events, by PT
- Number of subjects with adverse events leading to discontinuation of investigational product, by system organ class and preferred term.

In summaries including SOC or PT, the summaries will first be sorted by decreasing percentage of participants in each SOC and PT within SOC, and then alphabetically by SOC, and PT within SOC.

The following summaries for the number and percentage of adverse will be created:

- Number of adverse events by system organ class and preferred term.

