4.11.3 Clinical Laboratory Evaluation

All values will be classified as low (below range), normal (within range), or high (above range) based on central laboratory reference ranges.

The Na/K ratio will be calculated at each timepoint and this ratio will be included in clinical chemistry listings and tables. All clinical laboratory results will be listed.

The comparison of the effect of treatment on changes in Na, K and Na/K will be analysed by means of the same statistical model as that used for the analysis of the primary endpoint.

For haematology, clinical chemistry and coagulation a table with descriptive statistics of absolute values and changes from baseline for each laboratory variable over time. Only planned tests will be summarized. In the case of the urinalysis, individual measurements will be listed and a summary table

of the baseline versus maximum value on-treatment (ie, a shift table) will be created.

The on-treatment definition will be based on the on-treatment definition used for AE.

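### SAP 4.3.2.1 rule 1 starts the on-treatment window where every other rule ends it, and the urinalysis and ECG summaries may inherit that wording.

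*SAP*

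**What the plan says.** SAP 4.3.2.1 lists the rules that decide whether an AE is on-treatment. Rule 1 reads: "An AE starting from last dose plus 21 days will be considered on-treatment". Rule 2 deals only with incomplete start dates. It counts such an event unless the known date parts show that "the start date falls outside the time from dosing on Day 1 to last dose plus 21 days".

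SAP 4.11.1 assigns an AE to a treatment "if the start of the AE is after the first dose of the treatment but before the end of 21 days after the last dose", and explains the limit as "the end of Day 24, in the case of subjects whose last dose was on Day 3". It adds: "AEs occurring prior to the time of dosing on Day 1 and after 21 days after the last dose will not be included in summaries". Protocol 9.4.3.1 also starts its summaries at the first dose and closes them at 21 days: "AEs occurring after 21 days will be listed separately, but not included in summaries".

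SAP 4.11.3, which includes a urinalysis table of baseline against the largest on-treatment value, states: "The on-treatment definition will be based on the on-treatment definition used for AE". The ECG part of SAP 4.11.4 repeats that sentence. Neither names the section it refers to.

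**The concern.** Rule 1 gives neither a first-dose bound nor an upper bound. Rule 2 cannot repair it for fully dated events, because rule 2 covers incomplete dates only. Read as written, the rule for the ordinary case points at the period after the one that the rest of the plan describes.

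The cross-references make this more than a slip of wording. Section 4.3.2.1 is the only place where an AE rule carries the on-treatment label; 4.11.1 never uses the term. A programmer who follows the label from 4.11.3 or 4.11.4 arrives at the faulty rule. Safety and tolerability against prednisolone is a stated objective, so the observations entering those summaries should not depend on which section was coded.

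**Working it through.** **Inputs.** Dosing is on Days 1 to 3 of each period (SAP 3.1). The follow-on window is 21 days (SAP 4.3.2.1 and 4.11.1, protocol 9.4.3.1). Period 2 dosing is on study Days 28 to 30, and the final visit is 30 ± 4 days after last dose (SAP 6.1). Urinalysis is scheduled on Days -2, 1, 4, 26, 28 and 31 and at the final visit. ECGs are on Days 1, 4, 28 and 31 and at the final visit, with Days 1 and 28 recorded pre-dose and 1.5 hours post-dose (SAP 6.1; screening left aside).

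**Step 1: the plan's own figure.** Last dose Day 3 + 21 = Day 24. This reproduces the end of the window given in 4.11.1.

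**Step 2: the window in rule 2, 4.11.1 and the protocol.** Day 1 to Day 24, or 24 - 1 + 1 = 24 calendar days.

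**Step 3: rule 1 as written.** Start day ≥ 3 + 21 = 24, with no end. Cut off for illustration before period 2 dosing on Day 28, it covers Days 24, 25, 26 and 27. The overlap with step 2 is Day 24 alone.

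**Step 4: scheduled assessments.** Each is judged against the last dose of its own period (Day 3 or Day 30).

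| Assessment | Days since last dose | Rule 1 as written | First dose to last dose + 21 |
|---|---|---|---|
| Day 1, post-dose ECG | 1 - 3 = -2 | out | in |
| Day 4, urinalysis and ECG | 4 - 3 = 1 | out | in |
| Day 26, admission urinalysis | 26 - 3 = 23 | in | out |
| Day 28, post-dose ECG | 28 - 30 = -2 | out | in |
| Day 31, urinalysis and ECG | 31 - 30 = 1 | out | in |
| Final visit, urinalysis and ECG | 26 to 34 | in | out |

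No row is in under both. In period 1 no ECG is scheduled on Days 24 to 27. The first one past the literal cut-off is the Day 28 pre-dose recording, 28 - 3 = 25 days after last dose, which SAP 4.8 uses as the period 2 baseline.

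**Step 5: a charitable reading.** Suppose rule 1 means from the last dose up to 21 days later. With last dose on Day 3 the window is Days 3 to 24, which still omits Days 1 and 2.

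**The case against.** The best defence is that rule 1 is an obvious drafting omission. Rule 2 on the next line, the concomitant-medication rules in the same section, 4.11.1 and the protocol all run from first dose to 21 days after last dose, and rule 1 is the lone outlier. Rule 1 also does not say that only such events count. The reference in 4.11.3 and 4.11.4 can be read as pointing to 4.11.1, the section headed Adverse Events. Finally, SAP 4.3.1 defines the last dose, for counting days since dosing, as the one immediately before the event; with that meaning, the charitable reading in step 5 would recover Days 1 and 2.

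Much of this stands. An omission is the likely explanation, and inheritance by 4.11.3 and 4.11.4 is possible rather than certain. It does not remove the defect. The lead-in says that these rules settle whether or not an event is on-treatment, the charitable reading adds words that are absent, and its result depends on which meaning of last dose applies.

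A reader might infer that rule 1 decides what enters every AE table and fully reverses the safety window. The documents do not support that. Section 4.11.1 sets its own window for the AE summaries, bars later events from them, and does not refer to 4.3.2.1. Day 24 lies inside both windows, so the reversal is not complete. Nor are laboratory shift tables in general exposed: 4.11.3 specifies a shift table for urinalysis only, while haematology, chemistry and coagulation get descriptive statistics over time.

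**Conclusion.** The point holds as an internal contradiction in operative SAP text that should be corrected. Rule 1 as written yields a window that meets the intended one on a single day, Day 24. For the AE summary tables, the consequence is two competing rules, with the right one stated in the section that governs them. For the urinalysis shift table and any on-treatment ECG summary, the unnumbered cross-reference leaves a real route to the wrong rule. If it is taken, every scheduled on-treatment value in the step 4 table is lost and values more than 21 days after dosing replace them.

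This rests on the nominal schedule with the last dose on Day 3 of each period. It does not show that any output was programmed this way. The primary endpoint, power and alpha are not touched.

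**What to change.** Reword rule 1 in SAP 4.3.2.1 so that an AE is on-treatment when it starts from the first dose in a period up to the last dose in that period plus 21 days. State there that 4.11.1 is the single definition. In 4.11.3 and in the ECG part of 4.11.4, cite 4.11.1 by section number.

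The cost is one sentence and two cross-references. No new rule is introduced, since this is the window already in rule 2, 4.11.1 and the protocol. If the urinalysis or ECG outputs have already been programmed, check which window was coded.

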- **Cohort 3:** participants will be randomised in a ratio of 1:1 to receive placebo and prednisolone over two 72-hour periods in a cross-over design (placebo followed by 5 mg prednisolone [AB sequence group] or 5 mg prednisolone followed by placebo [BA sequence group]). There will be a 3-week Wash-out period between treatment periods. (N = 8 completed [4 in each sequence group].)

With the exception of the SoA, where the headings of visits 4 and 5 include both the day within the study and within each period (such as 26 and -2 for the same day), all days in this document refer to days within each period. As an illustration, Day 28 in the study is only referred to as Day 1 in this document.

In treatment period 1, participants will be fitted with a continuous glucose monitoring/flash glucose monitoring (CGM/FGM) device on Day -4 on an Out-patient' basis. Within each treatment period, participants will be admitted to the CRU on Day -2. On Day -1, they will have a baseline MMTT. Dosing of IMP will occur on Days 1 to 3. The CGM/FGM device will be removed on Day 4.

Participants will have an MMTT in the morning of Day 4, before being discharged from the CRU in the afternoon of Day 4.

3.2 Variables associated to the different endpoints.

As stated in section 3.1, Days refer to those within each treatment period (eg, Days 24, 26, 27, 28, 39, 30, 31 in the study referred to as Day -4, -2, -1, 1, 2, 3 and 4).

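### The rule for adverse events with incomplete start dates uses only start and end dates and runs once per period, so one event can be charged to both treatments and an event reported before dosing can count as on-treatment

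*SAP*

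**What the plan says.** SAP 4.3.2.1 does not impute incomplete dates. Rule 2 starts from "An AE with an incomplete start date and whose end date is not prior to the time of dosing on Day 1". Such an AE "will be considered to have taken place on-treatment unless the non-missing components of the incomplete start date indicate that the start date falls outside" the window from dosing on Day 1 to last dose plus 21 days. The same section adds that "AEs and medications with completely missing end dates will be assumed to be ongoing".

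Day 1 belongs to a period. SAP 3.1 states that "all days in this document refer to days within each period" and gives the example that "Day 28 in the study is only referred to as Day 1 in this document". SAP 4.3.1 agrees: "Study day 1 is defined as the date of first dose of study treatment within each treatment period".

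SAP 4.11.1 attributes events to treatments by start date: "AEs will be assigned as having taken place after each of the two treatments if the start of the AE is after the first dose", provided that the start is also within 21 days of that treatment's last dose. It spells out this limit as "the end of Day 24, in the case of subjects whose last dose was on Day 3". It keeps AEs from before Day 1 dosing out of the summaries, and protocol 9.4.3.1 does the same. Its only provision for a partial date is a missing start time on Day 1.

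**The concern.** In a two-way crossover, each AE that starts on treatment should be charged to one treatment. With complete dates the SAP achieves this, because the two windows do not overlap. With an incomplete date rule 2 decides, and it has two gaps.

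- **No tie-break.** If the known date parts fit both windows, and the event is ongoing or has no end date, the event meets the rule in both periods.
- **No use of the reporting date.** AEs are collected from consent and asked about visit by visit. An event can therefore be on file before the first dose and still be classed as on-treatment, because its recorded month also contains dosing days.

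The AE tables by treatment serve the safety objective of comparing AZD9567 with prednisolone. Two of the three cohorts have eight planned completers, so one event in the wrong column is visible there.

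**Working it through.** **The plan's own figure.** Last dose on Day 3 plus 21 days gives Day 24, as SAP 4.11.1 states.

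**The windows in study days.**
- Period 1: Day 1 to Day 24, which is first dose to first dose + 23 days.
- Period 2: starts on study Day 28 (SAP 3.1) and ends on 28 + 23 = Day 51, which is first dose + 27 to + 50 days.
- Gap: Days 25 to 27, three days. Complete dates cannot fall in both windows.
- Extended washout (footnote b of the Schedule of Activities allows 4 weeks instead of 3): Period 2 starts 7 days later.

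**Example of double assignment.** With first dose on 2 March 2021, the windows are 2 to 25 March and 29 March to 21 April. An ongoing AE with start March 2021 fits both windows, and its end date precedes neither Day 1. It is on-treatment under both treatments.

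**Example of a pre-dose event.** With first dose on 10 March 2021, Day -4 is 6 March. An ongoing AE recorded that day with start March 2021 fits the Period 1 window (10 March to 2 April). It is counted, although it was on file four days before dosing. It does not fit the Period 2 window (6 to 29 April), so it enters one column only.

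**How often a month is ambiguous.** I assumed that only month and year are known and that first-dose dates are spread evenly, and enumerated every first-dose date in 2021 (365 dates).

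| Quantity | 3-week washout | 4-week washout |
|---|---|---|
| Days in either window (365 × 48) | 17,520 | 17,520 |
| of these, in a month touching both windows | 8,592 (49.0%) | 4,766 (27.2%) |
| Days in the 14 days before first dose (365 × 14) | 5,110 | 5,110 |
| of these, in a month touching the Period 1 window | 3,850 (75.3%) | 3,850 (75.3%) |
| of these, in a month touching both windows | 54 (1.1%) | 0 |

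The planned calendar gives nearly the same shares. With first doses from September 2020 to March 2021, they are 48.8% and 27.0% for the windows, and 75.2% for the 14 days before dosing.

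**Conditions on these shares.**
- A Period 1 onset is counted twice only if the AE is also ongoing, or lacks an end date, at Period 2 dosing. A known end date before then keeps it out of Period 2.
- For a Period 2 onset the end-date test gives no protection, because its end date always falls after Period 1 Day 1.
- A pre-dose event must still be ongoing, or lack an end date, at dosing.

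**Effect on a table row.** One participant is 1/24 = 4.2 points in Cohort 1 and 1/8 = 12.5 points in Cohorts 2 and 3, using planned completers. The AE tables use everyone dosed, so the denominator may be slightly larger. The row moves only if that participant is not already counted in it.

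**The case against.** The strongest objection is that the problem may never arise. Start date and time are collected for every AE, participants live in the unit from Day -2 to Day 4, and each contact asks about the time since the last one. Partial dates may be rare or absent, and nothing in the documents says which intervals would produce them. Counting an event of uncertain onset as on-treatment is a cautious default. The safety analysis is descriptive, so no test is distorted. The data review meeting before unblinding (SAP 4.5.2) covers AEs and could settle such cases. All of this limits the size of the point. It does not remove it: rule 2 is the only rule for incomplete start dates, the exclusion of pre-dose AEs does not say how it applies to them, and no instruction is given to the meeting.

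One might read Day 1 as the first dose of the whole study. SAP 3.1 rules that out, and a single window would still not say which treatment the event belongs to.

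It is tempting to infer that pre-dose events are added to both columns and so make the treatments look alike. The enumeration does not support this. Only about 1% of the 14 pre-dose days lie in a month touching both windows. Such an event almost always enters the column of the first treatment received, and sequence is randomised 1:1, so it adds misclassification and does not pull the treatments together. It is equally tempting to read 49% as a share of AEs. It is a share of calendar days, and it applies only to month-only dates.

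**Conclusion.** The gap is real and minor. As written, rule 2 can charge one AE to both treatments, and it can put into the summaries an AE reported before dosing, which SAP 4.11.1 and protocol 9.4.3.1 exclude. The double charge does not look intended. SAP 4.10 says openly that medications ongoing in both periods count in both, and nothing similar is said for AEs.

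The size is conditional. If dates are month-only and first-dose dates are evenly spread, about 49% of on-treatment days are ambiguous between periods (about 27% with the longer washout), and about 75% of the 14 days before first dose cannot be told from Period 1 by month. How many AEs this touches is unknown and may be none. The effect of one misassigned participant is at most about 4 points in Cohort 1 and 12.5 points in Cohorts 2 and 3. The documents support no claim of a systematic bias towards similarity from pre-dose events.

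**What to change.** Add to rule 2, in this order:

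- (a) An AE that the study records show was reported before the first dose of a period is not on-treatment for that period.
- (b) An AE reported before the Period 1 first dose is listed only.
- (c) An AE first reported after the Period 1 first dose and before the Period 2 first dose can be assigned to Period 1 only, and only if its known date parts fit Day 1 to last dose plus 21 days. Otherwise it is listed only.
- (d) An AE first reported after the Period 2 first dose that fits both windows is counted once, under Period 2, and flagged.

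The date or visit of first report is not among the AE variables listed in protocol 8.4.2 and SAP 3.2.2. The sponsor should confirm that it can be derived from the eCRF or the EDC system. If it cannot, these cases should be resolved by blinded review at the data review meeting before unblinding, and the SAP should say so.

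The cost is a few lines of SAP text and, if the date can be derived, a small programming change. The downside is that a Period 1 event reported late may be placed in Period 2, but it is counted once and flagged.
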